- 1) Perform a physical examination and record the subject's axillary temperature
- 2) Collect and check the information entered into the DC1 by interviewing the subject / subject's parent (s) / legally acceptable representative(s) and request information concerning any medical event, serious or not, that may have occurred since Visit 1
- 3) Check concomitant medications and record every reportable medication
- 4) Remind the subject / subject's parent(s) / legally acceptable representative(s) to call the study center if a serious medical event occurs
- 5) Arrange an appointment for Visit 3 (365 days [+/- 20 days] after Visit 1)
- 6) Complete the source documents and relevant CRF pages for the visit

Telephone Calls 1 and 2 (2 months and 4 months [+ 8 day window] after Visit 1)

The Investigator or authorized designee will:

- 1) Ask if the subject has experienced any SAEs not yet reported. If an SAE occurred, follow the instructions in [Section 10](#) for reporting it
- 2) Remind the subject / parent / legally acceptable representative to notify the site in case of an SAE

Visit 3 (180 Days [± 20-day Window] After Visit 1)

The Investigator or designated study personnel will:

- 1) Perform a physical examination and record the subject's axillary temperature
- 2) Review for any contraindications
- 3) Perform a urine pregnancy test (pre-injection) (women of childbearing potential only)
- 4) Check concomitant medications and record every reportable medication ongoing at the time of vaccination

- 5) **For all subjects:** collect the blood sample (BL2, 5 mL) for neutralizing Abs and record the date of collection (see [Section 7.1.1](#) for detailed instructions on the handling of blood samples)

Note: If the attempt(s) to collect blood is (are) unsuccessful, the subject should be given the opportunity to return to the study site for another attempt within the visit window. If a blood sample cannot be obtained, the reason will be recorded in the blood sampling page of the eCRF.

- 6) Contact IVRS/IWRS to obtain the dose number to be administered
- 7) Inject the appropriate study vaccine into the opposite limb from the limb the vaccination was administered to in Visit 1
- 8) Record the date of injection, the site and side of injection and the route of administration, as well as the dose number of the vaccine
- 9) Affix the vaccine labels in the subject's source documents

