12.2 Analysis Sets

12.2.1 Per-Protocol Analysis Set

The Per-Protocol analysis set (PPAS) will include all subjects who had no protocol deviations and will be defined for both stages as follows:

STAGE I:

The subjects who will be vaccinated but who meet any of the following study violations will be excluded from the PPAS in STAGE I:

- Subject did not meet all protocol-specified inclusion/exclusion criteria or definitive contraindications
- Subject did not receive the correct number of doses or injections
- Subject received a vaccine other than the one that he/she was randomized to receive
- Administration of vaccine at V05 was not done as per protocol (site and route of administration)

- Subject did not receive vaccine at V05 in the proper time window defined in the tables of the study procedures
- Subject did not provide a V06 post-dose serology sample in the proper time window
- Subject received a protocol-restricted medication, therapy, or vaccine in STAGE I as defined in Section 6.7.
- Subject's post-injection serology samples at V06 did not produce a valid test result (ie, a result different from "not-reportable" ['NR'] or missing, for at least one dengue serotype)

STAGE II:

The subjects who will be vaccinated but who meet any of the following study violations will be excluded from the PPAS in STAGE II:

- Subject did not meet all protocol-specified inclusion/exclusion criteria or definitive contraindications
- Subject did not receive the correct number of doses or injections
- Subject had negative serostatus at baseline dengue status.
- Subject received a vaccine other than the one that he/she was randomized to receive
- Administration of vaccine at V07 was not done as per protocol (site and route of administration)
- Subject did not receive vaccine at V07 in the proper time window defined in the tables of the study procedures
- Subject did not provide a V10 post-dose serology sample in the proper time window
- Subject received a protocol-restricted medication, therapy, or vaccine in STAGE II as defined in Section 6.7 of the protocol
- Subject's post-injection serology samples at V10 did not produce a valid test result (ie, a result different from "not-reportable" ['NR'] or missing, for at least one dengue serotype)
- Subjects randomized to Group 1 not included in the PPAS in STAGE I

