5.2.1 Per-Protocol Analysis Set

The per-protocol analysis set (PPAS) will include all subjects who had no protocol violations as defined below and will be defined for both stages as follows:

STAGE I:

The subjects who will be vaccinated but who meet any of the following study violations will be excluded from the PP set in STAGE I:

- Subject did not meet all protocol-specified inclusion/exclusion criteria or definitive contraindications
- Subject did not receive the correct number of doses or injections
- Subject received a vaccine other than the one that he/she was randomized to receive
- Administration of vaccine at V05 was not done as per protocol (site and route of administration)
- Subject did not receive vaccine at V05 in the proper time window (V01 +365 days \pm 20 days) defined in the tables of the study procedures
- Subject did not provide a V06 post-dose serology sample in the proper time window (V05 +28 days \pm 14 days)
- Subject received a protocol-restricted medication, therapy, or vaccine in STAGE I as defined in Section 6.7 of the protocol.
- Subject's post-injection serology samples at V06 did not produce a valid test result (i.e. a result different from "not-reportable" ['NR'] or missing, for at least one dengue serotype).

STAGE II:

The subjects who will be vaccinated but who meet any of the following study violations will be excluded from the PPAS in STAGE II:

- Subject did not meet all protocol-specified inclusion/exclusion criteria or definitive contraindications
- Subject did not receive the correct number of doses or injections
- Subject had negative dengue serostatus at baseline.
- Subject received a vaccine other than the one that he/she was randomized to receive
- Administration of vaccine at V07 was not done as per protocol (site and route of administration)
- Subject did not receive vaccine at V07 in the proper time window defined in the tables of the study procedures
- Subject did not provide a V10 post-dose serology sample in the proper time window
- Subject received a protocol-restricted medication, therapy, or vaccine in STAGE II as defined in Section 6.7 of the protocol.
- Subject's post-injection serology samples at V10 did not produce a valid test result (i.e. a result different from "not-reportable" ['NR'] or missing, for at least one dengue serotype).
- Subjects randomized to Group 1 not included in the PP set in STAGE I

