5.2.5 Populations Used in Analyses

The PPAS will be used for the analysis for the primary objectives. The FAS will be used for the superiority hypotheses testing for secondary objectives. All other immunogenicity analyses will be performed on the FAS.

The SafAS will be used for the description of clinical safety.

Enrolled subjects and randomized subjects will be used for various standard population tables including duration of the study, disposition of participants and deviations. Demographic and baseline characteristics will be presented on the PPAS and FAS.

The AIT subset will be used to describe additional neutralizing Ab levels in this subset, Ab specificity and affinity maturation, and CMI responses.

^a for which safety data are scheduled to be collected

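### The Stage I per-protocol set checks injection window and site/route at V05 only, so a subject with an off-schedule or wrongly administered V03 injection stays in the primary non-inferiority analysis

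*SAP*

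**What the plan says.** SAP 5.2.5 sets the population: "The PPAS will be used for the analysis for the primary objectives". SAP 5.2.1 defines that set by a closed list. It "will include all subjects who had no protocol violations as defined below". Protocol 12.2.1 opens more broadly ("will include all subjects who had no protocol deviations") but then gives the same list.

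The Stage I items that concern injections are:

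- **Timing:** "Subject did not receive vaccine at V05 in the proper time window" (SAP 5.2.1, which adds the figures: V01 + 365 days, ± 20 days). Protocol 12.2.1 has the same item: "Subject did not receive vaccine at V05 in the proper time window defined in the tables of the study procedures".
- **Site and route:** "Administration of vaccine at V05 was not done as per protocol (site and route of administration".
- **All injections:** "Subject did not receive the correct number of doses or injections", plus a separate item on receiving a product other than the one randomized.

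V03 appears nowhere in the list. Yet V03 has its own window: Protocol 5.1.4 heads the visit "Visit 3 (180 Days [± 20-day Window] After Visit 1", and the procedures tables in both documents agree. Under the schedules in SAP 3.1, the V03 injection is the first vaccine dose in Group 2 and the second in Group 1.

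**The concern.** Stage I compares a 2-dose with a 3-dose schedule, with injections specified 6 months apart. A per-protocol set for that comparison would be expected to hold subjects who received the schedule. Here a Group 2 subject can have received the two vaccine doses at an interval far from the planned one, or the first by the wrong site or route, and still count as per protocol.

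No other planned immunogenicity analysis covers the gap. The full analysis set, used for the superiority tests and the descriptive GMRs, does not screen V03 timing either, and no analysis by dosing interval is planned. What is at stake is whether the primary population matches the regimens named in the primary objectives, at both the 28-day and the 1-year comparison.

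**Working it through.** **1. The criteria, taken one at a time.** Take a Group 2 subject injected at V03 on day 300 and at V05 on day 365, both correctly counted from V01, with V06 on time.

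| Stage I exclusion (SAP 5.2.1) | Does it remove this subject? |
|---|---|
| Eligibility or definitive contraindication | No |
| Number of doses or injections | No, all three were given |
| Wrong product | No |
| Site and route at V05 | No |
| V05 window, day 345–385 | No, day 365 |
| V06 sample window | No |
| Restricted medication, therapy or vaccine | No |
| No valid V06 result | No |

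The interval between the two vaccine doses is 365 − 300 = 65 days, and the subject stays in.

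**2. The range of intervals.** Inputs: V03 at 180 ± 20 days (day 160–200) and V05 at 365 ± 20 days (day 345–385), both counted from V01.

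- Nominal interval: 365 − 180 = 185 days.
- Both windows kept: shortest 345 − 200 = 145 days; longest 385 − 160 = 225 days.
- PPAS rules as written: V05 lies in day 345–385 and V03 anywhere between V01 and V05. The interval is above 0 and below 385 days. An in-window V05 does not constrain it, because V05 is counted from V01.

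**3. A conflict in the visit instructions.** Under Visit 2, Protocol 5.1.4 tells sites to book Visit 3 at 365 ± 20 days after Visit 1; the Visit 3 heading and the procedures table say 180 ± 20. If a site followed the Visit 2 text and V05 fell in its own window, the interval could be at most 385 − 345 = 40 days, and the subject would pass every item in the table above.

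**4. Effect on the GMR (assumptions only).** Let f₁ and f₂ be the off-schedule fractions in Groups 1 and 2, and d₁ and d₂ the resulting mean shifts in log10 titer. The log10 GMR then moves by f₂d₂ − f₁d₁. None of the four quantities is in the documents. With f₁d₁ = 0, so that only Group 2 is affected:

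- f₂ = 2%, 1.5-fold titer difference: 0.02 × log10(1.5) = 0.0035, or 1.2% of the 0.301 margin.
- f₂ = 10%, 3-fold difference: 0.10 × log10(3) = 0.0477, or 15.8% of the margin.

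In ratio terms the Group 2 GMT moves by a factor of 1.01 to 1.12. Similar shifts in Group 1 would offset part of this.

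**5. Power cost of adding the criteria.** The planning numbers first: 350 × 0.85 = 297.5 per group against the stated 296, and 1050 × 0.85 = 892.5 against 888. These agree closely, not exactly. The power figures cannot be recomputed because an assumption behind them is redacted, so I interpolated linearly in SAP Table 5.2, assuming that 2–10% more subjects are excluded from each group. For example, 235 × 0.98 = 230.3, giving 83.54 + (230.3 − 207)/(235 − 207) × (89.22 − 83.54) = 88.3%.

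| n per group | Stated 1-year power | 2% fewer | 10% fewer |
|---|---|---|---|
| 296 | 95.2% | 94.8% | 93.3% |
| 235 | 89.2% | 88.3% | 84.5% |
| 207 | 83.5% | 82.4% | 77.9% |

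**The case against.** **The protocol already excludes any deviation.** Its opening words could be read that way, but they lead into the same V05-only list, and the SAP confines exclusions to the violations it lists. SAP 5.7 does not record that narrowing. At best the rule is ambiguous.

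**V03 is bounded in practice.** This stands in part. V03 has its own window, and Protocol 5.2.7.1 requires postponed vaccinations to stay within the procedures-table timeframe. The day-300 example is a gross departure, and nothing shows that such cases are expected. But these are conduct rules, and a per-protocol set exists to deal with departures from them.

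**A problem would be seen elsewhere.** Deviations are tabulated (SAP 5.2.5) and a blinded data review precedes database lock (Protocol 11.3, SAP 5.6). That gives visibility but does not change who is in the primary analysis.

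**Stronger readings to avoid.** A reader might infer that injections before V05 go unchecked. They do not: a missed injection or wrong product at V03 is already excluded. A reader might also infer that keeping off-schedule subjects favours non-inferiority by blurring the difference. The documents do not support that. They do not say how interval affects titer, and if a shorter interval lowered Group 2's titers, keeping those subjects would make non-inferiority harder to show. V03 is also an active dose in both groups, and assignment is randomized, stratified by site and age, and observer-blind. Scheduling errors should therefore be similarly frequent in each group and their effects may partly cancel, though not necessarily fully, since Group 1 also has a vaccine dose at V01.

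**Conclusion.** The gap holds on the text. The Stage I PPAS checks dose count and product at every injection but window and site/route at V05 only, so a subject with a V03 injection outside its window, or wrongly sited or routed, remains per protocol. The set admits V03-to-V05 intervals above 0 and below 385 days, where the two protocol windows together allow 145–225.

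The direction and size of any effect on the GMR cannot be derived from the documents. Under the assumed ranges in the working, with only Group 2 affected, the shift is about 1–16% of the margin; it would be less if Group 1 is affected similarly. It is probably small. This is a cheap improvement to the definition of the primary population, not evidence that the primary result would be biased.

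**What to change.** Add two Stage I exclusions to SAP 5.2.1, applied identically to all groups and fixed before unblinding: V03 injection outside the procedures-table window, and V03 administration not per protocol for site and route. Record them in SAP 5.7 as a change from Protocol 12.2.1, and reconcile the two opening sentences of the PPAS definition at the same time.

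Reconcile the Visit 2 booking instruction in Protocol 5.1.4 (365 days) with the Visit 3 heading and procedures table (180 days), so that the window used by the new criterion is unambiguous. Which interval was intended is for the sponsor to state.

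No new data are needed, since Protocol 5.1.4 already has the date, site and route of the V03 injection recorded. The price is a few more exclusions and the power loss tabulated above. Group 1 exclusions also carry into the Stage II PPAS, which requires Group 1 subjects to be in the Stage I set. If the sponsor prefers to leave the PPAS unchanged, a prespecified sensitivity analysis with the same two exclusions is the minimum.

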	
(one 1 year post-Injection 3, one 28 days after the Y1 booster injection, one 28 days after the Y2 booster injection, and one 6 months after the Y2 booster injection).
 
Assuming that \log_{10} transformation of the titers/ratios follows a normal distribution, first, the mean and 95% CI will be calculated on \log_{10} (titers/ratios) using the usual calculation for normal distribution, then antilog transformations will be applied to the results of calculations, to compute GMTs/GMTRs and their 95% CIs.
 
This will be a non-inferiority study in two STAGES. If non-inferiority is not achieved, assessments of immunogenicity will be descriptive.
 
There will be two non-inferiority tests comparing Group 2 to Group 1 in STAGE I:
 
 • at 28 days after last injection • at 1 year after last injection 
There will be 4 non-inferiority tests planned in STAGE II:
 
Within Group 1 comparisons:
 
 • Booster Group 1a vs post dose 3 Group 1a • Booster Group 1b vs post dose 3 Group 1b 
Between Group 1 comparisons:
 
 • Booster Group 2a vs post dose 3 Group 1 • Booster Group 2b vs post dose 3 Group 1 
Regardless of the outcome in STAGE I, the within Group 1 tests will be performed. However, the between Group 1 tests will only be performed for the Group(s) which demonstrated non-inferiority to Group 1 in STAGE I.
 
A. Hypothesis and Statistical Method for the Primary Objectives
 
STAGE I:
 
A non-inferiority testing approach will be performed for each serotype to show the non-inferiority of 2 doses of CYD dengue vaccine (28 days after last injection) compared to 3 doses of CYD dengue vaccine, in subjects seropositive at baseline. A Bonferonni alpha adjustment will be used to control for multiplicity.
 
The non-inferiority testing approach will also be performed for each serotype to show the non-inferiority of 2 doses of CYD dengue vaccine (1 year after last injection) compared to the 3 doses of CYD dengue vaccine, in subjects seropositive at baseline. A Bonferonni alpha adjustment will be used to control for multiplicity.
 
Individual hypotheses for each serotype will be as follows:
 $H_0^i: GMT_{Group\ j}^i / GMT_{Group\ 1}^i \leq \frac{1}{\delta}$ $H_1^i: GMT_{Group\ j}^i / GMT_{Group\ 1}^i > \frac{1}{\delta}$ 
Where: i=1, 2, 3, and 4 (each serotype), j=2

--	--

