- 1) Perform a physical examination and record the subject's axillary temperature
- 2) Review for any contraindications
- 3) Urine pregnancy test (pre-injection) (women of childbearing potential only)
- 4) Check concomitant medications and record every reportable medication ongoing at the time of injection
- 5) **For All Subjects:** Collect the fourth blood sample (BL4 for neutralizing Abs; see [Section 7.1.1](#) for detailed instructions regarding the handling of blood samples) and record the date of collection
- 6) Contact IVRS/IWRS to obtain the dose number to be administered
- 7) Inject the appropriate study vaccine into the opposite limb from the limb the injection was administered to in Visit 3
- 8) Record the date of injection, the site and side of injection and the route of administration, as well as the dose number of the vaccine
- 9) Affix the vaccine labels in the subject's source documents
- 10) Keep the subject under observation for 30 minutes, and record any injection site reactions or systemic events in the source documents and any reportable concomitant medications
- 11) Give the subject / subject's parent (s) / legally acceptable representative(s) the DC3 to record any injection site reactions and systemic AEs, together with instructions for its completion, including explanations on the definition and use of intensity scales for collection of AEs
- 12) Remind the parent/legally acceptable representative to bring back the DC when they return for Visit 6 at a specified date
- 13) Remind the subject / subject's parent (s) / legally acceptable representative(s) to call the study center if a serious medical event occurs
- 14) Arrange an appointment for Visit 6 (28 days [+ 14 days] after Visit 5)
- 15) Complete the source documents and relevant eCRF pages for this visit

Visit 6 (+ 28 days [+14-day window] after V05): Collection of Safety Information and Blood Sample

The Investigator or designated study personnel will:

- 1) Perform a physical examination and record the subject's axillary temperature
- 2) Check and collect the information entered into DC3 by interviewing the subject / subject's parent (s) / legally acceptable representative(s) and request information concerning any medical event, serious or not, that may have occurred since Visit 5
- 3) Check concomitant medications and record every reportable medication

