- 6) Remind the subject / subject's parent(s) / legally acceptable representative(s) to call the study center if a serious medical event occurs
- 7) Arrange an appointment for the next visit
- 8) Complete the source documents and relevant eCRF pages for this visit

^a BL7 or BL11: 20 mL will be drawn in adolescent subjects and 30 mL in adult subjects.

^b BL8 or BL12: 20 mL will be drawn in adolescent subjects and 30 mL in adult subjects.

**Visit 10 (Visit 7 + 28 days [+ 7-day window for AIT subset; + 14-day window for all subjects]):
Collection of Safety Information and Blood Sample**

The Investigator or designated study personnel will:

- 1) Perform a physical examination and record the subject's axillary temperature
- 2) Check concomitant medications and record every reportable medication
- 3) At V10 (Y1) check the information entered into DC4 for subgroup a;
At V10 (Y2) check the information entered into DC5 for subgroup b
by interviewing the subject / subject's parent (s) / legally acceptable representative(s) and request information concerning any medical event, serious or not, that may have occurred since Visit 7 or Visit 9
- 4) Record any injection site reactions or systemic events and reportable concomitant medications
- 5) Collect blood sample (BL9 or BL13, 5 mL) for neutralizing Abs and record the date of collection (see [Section 7.1.1](#) for detailed instructions regarding the handling of blood samples). The volume used for specificity and affinity testing in the AIT subset will be used also from this aliquot as applicable.
- 6) **For AIT subset only (60 subjects):** an additional volume of blood will be drawn (15 mL for adolescents and 25 mL for adults) to assess CMI (see [Section 7.1.2](#) for detailed instructions regarding the handling of CMI blood samples).
- 7) Provide MA2 to record any medical events from the booster vaccination, together with instructions for its completion
- 8) Remind the subject / subject's parent(s) / legally acceptable representative(s) to call the study center if a serious medical event occurs
- 9) Complete the source documents, relevant eCRF pages and the termination record for this visit

SAEs and AEs that are related to vaccination or that led to discontinuation:

At any time during the study, a subject who experiences an SAE or an AE must be followed until resolution of the event if *either* of the following is true:

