For evaluations of CMI Ab specificity and affinity maturation, blood samples will be taken from STAGE I subjects immediately before Injection 1 (specificity, affinity and CMI) and at 28 days following injection 3 (specificity and affinity).

During STAGE II, only subjects identified as seropositive at baseline and thus eligible to booster injection will continue to be part of the AIT subset. The sampling from these subjects will continue into STAGE II when samples will be drawn immediately before the booster injection, and at 7 days, 14 days, and 28 days post-booster injection for Ab specificity and CMI; Ab affinity maturation will be assessed only prior to and 28 days post-booster injection.

See Table 3.1 for details of study procedures

Table 3.1: Study procedures

Table of Procedures – STAGE I and STAGE II

Visit Number (V)	STAGE I							STAGE II*								
	V01	V02	V03	V04	V05	V06	6M FU (PC7)†	V06-Inf	V07 (Y1)	V07 (Y2)	V08 (Y1/Y2) (AIT only)	V09 (Y1/Y2) (AIT only)	V10 (Y1/Y2)	6M FU (PC)‡		
Trial timelines (Days/Months)	V01	V01+ 28d	V01+ 180d	V03+ 28d	V01+ 365d	V05+ 28d	last inj + 6M		V05+ 12M	V05+ 24M	V07+ 7d	V07+ 14d	V07+ 28d	V07+ 6M		
Time Windows (Days)		+14d	±20d	+14d	±20d	+14d	+20d		+60	+60	+3d	+7d	+14d; +7d AIT only)	+20d		
Informed Consent/Assent	√								√							
Information letter on baseline serostatus								√								
Inclusion/Exclusion Criteria	√															
Demography	√															
Contraindications	√		√		√				Subgroup a: V07 Y1 Subgroup b: V07 Y2							
Significant Medical History	√															
History of YF or JE Infection/Vaccination and/or Dengue Infection	√															
Physical Examination and Temperature§	√	√	√	√	√	√			subgroup a: V07 Y1 subgroup b: V07 Y2		√	√	√			
Urine Pregnancy Test (pre-injection)**	√		√		√											
Concomitant Therapy	√	√	√	√	√	√							√	√	√	
IVRS/IWRS Contact	√		√		√											
Injection	Inj. 1		Inj. 2		Inj. 3				Booster Inj. subgroup a: V07 Y1 subgroup b: V07 Y2							

STAGE I								STAGE II*						
Visit Number (V)	V01	V02	V03	V04	V05	V06	6M FU (PC7)†	V06-Inf	V07 (Y1)	V07 (Y2)	V08 (Y1/Y2) (AIT only)	V09 (Y1/Y2) (AIT only)	V10 (Y1/Y2)	6M FU (PC)‡
Trial timelines (Days/Months)	V01	V01+ 28d	V01+ 180d	V03+ 28d	V01+ 365d	V05+ 28d	last inj + 6M		V05+ 12M	V05+ 24M	V07+ 7d	V07+ 14d	V07+ 28d	V07+ 6M
Time Windows (Days)		+14d	±20d	+14d	±20d	+14d	+20d		+60	+60	+3d	+7d	+14d; +7d AIT only)	+20d
Blood Sampling††	BL1		BL2	BL3	BL4	BL5			BL6 (all subjects)	BL10 (subgroup b only)			BL9 or BL13‡‡	

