5.7 Changes in the Conduct of the Trial or Planned Analyses

The following parts written in SAP are the changes different from Protocol Amendment 1:

The definition of j had been clarified for the Overall hypothesis.

The definition of WHO criteria and the corresponding derivation method had been added for virologically-confirmed dengue cases.

Instead of presenting the number and percentage of subjects with hospitalized suspected dengue case, only the hospitalized virologically-confirmed dengue cases will be summarized.

The ANCOVA model will be tested in Year 1 (Group 2a and Group 3a vs. Group 1a) and Year 2 (Group 2b and Group 3b vs. Group 1b).

The definition of depleted and undepleted for Ab specificity had been added: undepleted is defined as BSA-control depleted sera and depleted is DENV depleted samples.

The definition of homotypic Abs had been changed based on recent research findings to a neutralizing antibody titer above 20 (1/dil) following DENV depletion. Heterotypic antibodies will not be analyzed.

Delete “If non-inferiority is not achieved in Primary Objective, assessments of immunogenicity will be descriptive.” The descriptive analyses will conduct anyway regardless of the non-inferiority is achieved or not.

The definition of successful conclusion at Stage I and Stage II separately was added for clarity. Bonferroni adjustment for multiple testing at 28 days and 1 year post-Inj3 between Group 2 and Group 1 was removed and the adjustment of power was added as illustrated in Section 5.5.

The age stratus (9-16, 17-45 and 46-50 years of age) were added in definition of age group.

The definition of AUC-MB was added.

Description and comparison of GM in seropositive subjects between age strata were added, both overall and within each Group. These will allow the assessment of immunogenicity profile by age strata.

The ANCOVA model was added for 28 days after injection 3 between age strata adjusting for baseline neutralizing Ab levels.

The ANCOVA model was added for 28 days post-booster between age strata adjusting for the pre-booster neutralizing Ab levels.

6 References List

- 1 Newcombe R.G., Two-sided confidence intervals for the single proportion: comparison of seven methods, *Statistics in Medicine*, (1998) 17, 857-872

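### The SAP per-protocol rule accepts V06 samples from day 14, against day 28 in the protocol and SAP Table 3.1, and sets no timing rule for the 1-year co-primary sample (BL6)

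*SAP*

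**What the plan says.** **V06 sample.** The Stage I exclusion list in SAP 5.2.1 has: "Subject did not provide a V06 post-dose serology sample in the proper time window (V05 +28 days \pm 14 days"). The sign is plus-or-minus. The protocol's own list (12.2.1) gives no figure and asks only for a sample in the correct window.

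The schedule is one-sided everywhere else. Protocol 5.1.4 heads the visit "Visit 6 (+ 28 days [+14-day window] after V05"), and the Visit 5 appointment line in that section agrees. In the protocol's Table of Procedures and in SAP Table 3.1, the row beginning "Time Windows (Days") shows +14d in the V06 column.

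**Neighbouring rule.** The line for the third injection, in the same SAP list, is "Subject did not receive vaccine at V05 in the proper time window (V01 +365 days \pm 20 days"). This matches the tables.

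**Declared changes.** SAP 5.7 opens with "The following parts written in SAP are the changes different from Protocol Amendment 1" and then lists the changes. Neither the V06 window nor any per-protocol rule is among them.

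**BL6.** The 1-year comparison is a Stage I primary objective, added by Amendment 1 (protocol 1.4). Protocol 12.2.4 and SAP 5.2.5 assign the per-protocol set to the primary objectives. The timing rules in the Stage I list cover the V05 injection and the V06 sample. None covers BL6, the sample drawn at V07 Year 1.

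**Stage II.** The protocol synopsis plans comparisons such as "Booster Group 2a vs post dose 3 Group 1". The Stage II list in SAP 5.2.1 excludes "Subjects randomized to Group 1 not included in the PP set in STAGE I". The post-booster visit is "Visit 10 (Visit 7 + 28 days [+ 7-day window for AIT subset; + 14-day window for all subjects"]) in protocol 5.1.4.

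**The concern.** The per-protocol set is the only set named for the primary non-inferiority tests, so its sample windows decide which titres are tested.

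For V06, an analyst working from the SAP list keeps a titre drawn on day 14. An analyst working from the visit tables excludes it. The 28-day co-primary test would then include titres taken up to two weeks before the scheduled time. Under SAP 5.1.1.1 that test also decides whether the Group 2 booster comparisons are run.

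The same V06 titres form the Group 1 post-dose 3 reference in Stage II. There the two sides of the comparison would carry different windows.

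For BL6, Amendment 1 promoted the 1-year comparison to co-primary, but the Stage I list still checks sample timing at V06 alone. A participant whose BL6 was drawn well outside the visit window stays in the primary 1-year analysis.

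**Working it through.** No sample-size or power calculation applies. The check is window arithmetic.

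Window = target day − early allowance to target day + late allowance. Length, counting both ends = early allowance + late allowance + 1.

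| Event | Visit tables | SAP 5.2.1 |
|---|---|---|
| V05 injection (from V01) | 365 − 20 to 365 + 20 = days 345–385; 20 + 20 + 1 = 41 days | days 345–385; 41 days |
| V06 sample (from V05) | 28 − 0 to 28 + 14 = days 28–42; 0 + 14 + 1 = 15 days | 28 − 14 to 28 + 14 = days 14–42; 14 + 14 + 1 = 29 days |
| V10 sample (from V07) | days 28–42, or 28–35 for the AIT subset | no figure printed |
| BL6 (from V05) | 12 months, +60 days | no Stage I rule |

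1. **Control.** The V05 figure in SAP 5.2.1 reproduces from the tables. The V06 figure does not.
2. **Size of the V06 difference.** 29 − 15 = 14 extra days, namely days 14–27. All of them precede the earliest scheduled day.
3. **Where V06 titres are used.** They enter the Stage I 28-day test. They are also the post-dose 3 reference in the Stage II tests: within-participant for 1a and 1b, and as the Group 1 comparator for 2a and 2b. The exclusion carried over for Group 1 applies the Stage I rule again in Stage II.
4. **Stage II windows side by side.** The booster sample is scheduled on days 28–42 (28–35 for AIT). The reference is accepted on days 14–42.
5. **BL6.** Taking 12 months as 365 days (an assumption), the +60 days in both tables and in the Visit 7 Year 1 heading gives days 365–425 (0 + 60 + 1 = 61 days). The appointment line in the Visit 6 procedures gives ±20 days, that is days 345–385 (20 + 20 + 1 = 41 days). The two share only days 365–385, or 385 − 365 + 1 = 21 days. A BL6 rule that simply points to the visit window would therefore still be ambiguous.
6. **Does another rule cover BL6?** The V07 line in the Stage II list concerns the booster injection and governs Stage II membership only. Subgroup b receives no injection at V07 Year 1. The protocol's definition opens by requiring no protocol deviations, but its list has no V07 Year 1 item for Stage I, and the SAP limits the relevant violations to those it lists.

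**The case against.** **The wider V06 window may be deliberate.** Unlike the V05 line, the V06 line does not point to the tables. This cannot be ruled out, but SAP 5.7 is silent and SAP Table 3.1 keeps +14. The sign is worth checking against the source SAP before editing. If a wider window is meant, it needs to be declared.

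**Early samples may be few or absent.** Visit 6 is booked from day 28, so a draw on days 14–27 is already a departure from schedule. This stands. A reader might take 29 days against 15 as a doubling of exposure, or infer that most primary tests are compromised because V06 feeds the 28-day test and all the Stage II tests. Those figures describe where the rule reaches, not how many titres it changes.

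**Stage I comparisons are symmetric.** Groups 1 and 2 are randomised, observer-blind and share the same visit windows. This stands, so a reader should not infer a biased Stage I ratio. The asymmetry argument is confined to Stage II.

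**BL6 timing is not wholly unwatched.** Deviations are tabulated and data are reviewed blind before database lock (SAP 5.2.5, 5.6). The protocol's background also describes titres as stabilising after the first year, so a somewhat late BL6 may matter less than an early V06. Both points reduce the likely effect. Neither removes an out-of-window BL6 from the primary set.

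**The full analysis set gives a second look.** It supports descriptive ratios at both times and, if non-inferiority is met, superiority tests. It has no BL6 timing rule either.

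**Conclusion.** Both parts hold as faults in the written rules and should be fixed. The V06 rule in SAP 5.2.1 contradicts the protocol and the SAP's own table by 14 days on the early side, with no declared change. The primary set for the 1-year test has no timing rule for the sample it tests.

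The effect is unknown. The documents do not give the number of samples on days 14–27, the number of out-of-window BL6 samples, or whether early titres would run higher or lower. No bias in any ratio and no change in power is shown.

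Two stronger inferences are not supported:

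- A reader might infer that the 1-year test also needs a BL6 validity rule. Missing titres are not imputed (SAP 5.3.1), so a participant without a reportable BL6 titre contributes nothing to the test, and such a rule would change no estimate.
- A reader might infer that the 1-year test needs its own population because a failed V06 sample removes a good BL6. One common set for both co-primary tests is a defensible choice.

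The conclusion rests on the plus-or-minus sign being as printed in SAP 5.2.1, and on the listed exclusions being the complete operating rules.

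**What to change.** 1. In SAP 5.2.1, set the V06 sample window to 28 days after V05 with 14 days' allowance on the late side only, to match the protocol and SAP Table 3.1. If a wider analysis window is intended, list it in SAP 5.7 with its justification.
2. In protocol 12.2.1 and SAP 5.2.1, add that for the 1-year test BL6 must fall within the V07 Year 1 window of the procedures tables. First reconcile the ±20 days in the Visit 6 appointment line with the +60 days in the tables and the Visit 7 Year 1 heading.

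The cost is one symbol, one added rule in each document and one scheduling reconciliation. No new data are collected. The downside is that a few participants may leave the primary sets.
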